7.7 QUALITY CONTROL/DATA QUALITY

Optum's research approach centers on judicious scientific rigor and accuracy. In particular, Optum focuses on quality results at each step of the process.

- Optum develops study approaches of sound scientific design that meet clinically stringent review. Researchers develop detailed protocols that include definitions, codes, analyses, and table shells. The coding strategy is then reviewed by a clinical team member for validity and relevance. The protocol further provides Optum and BI an opportunity to solidify research questions and address any potential gaps in information.
- Code lists are developed by clinical coding experts and reviewed by Optum research teams during protocol development and review. Optum does not warrant that code lists accurately reflect how the codes are used in clinical practice and does not consider proposed code lists final until the client has carefully checked and approved them for use. [It is the client's responsibility to check code lists carefully before approving the final protocol.](#) Additional timeline and effort for code list exploration during dataset construction can be incorporated into projects for an additional fee. Changes to the project code lists following protocol approval will result in additional timeline and fees.
- A study is only as good as the data set created for analysis. Therefore, Optum incorporates meticulous quality assurance checks during data set construction to generate the most accurate data set. Our analysts perform record-level verification of data elements, double-program certain portions of the data set, program data edit checks, visually review raw claims data against the constructed data elements and review the analysis to assess the validity of results.
- Analysis is performed by a statistician or senior analyst under the supervision of the project director. The project director reviews output for consistency with the analysis plan and for quality and accuracy. Results are then reviewed with BIPI.
- The final deliverables receive internal review by a clinical consultant and/or by another senior researcher for quality and completeness.
- In addition to our meticulous internal quality processes, Optum has specific internal standard operating procedures (SOPs) for retrospective research that are monitored

continuously by the organization. Copies of SOPs can be viewed upon request, which include:

- Study Reports for HEOR Studies
- Statistical Analysis Plan (SAP) Development for HEOR Studies
- Costing for HEOR Studies
- HEOR Analytic Data Creation and Validation for Outcomes Studies
- Protocol Development for HEOR Studies
- Secure Delivery of Protected Health Information (PHI) and/or Personally Identifiable Information (PII) to External Parties by HEOR
- Data Collection Tool Development for HEOR Studies - US

7.8 LIMITATIONS OF THE RESEARCH METHODS

This study should be considered in the context of its limitations. First, identification of patients with newly diagnosed fibrosing ILD will rely on application of a claims-based algorithm. Presence of a diagnosis code does not necessarily indicate presence of disease; however, to limit misidentification of ILD patients, a confirmatory diagnosis will be required. Further, patients without ILD diagnosis in the 12-month baseline will be considered newly diagnosed. However, it is possible that patients with prevalent ILD who have not sought frequent care for their condition may be misclassified as newly diagnosed ILD patients.

Second, this study will utilize both claims and EHR data available in Optum's Market Clarity Integrated Claims + Clinical database to capture ILD symptoms, pulmonary function testing results, and hypoxemia. EHR data will be available for only a subset of the identified population; for remaining patients, these values will rely on information available in claims. Further, the analysis will rely on the availability of valid values (e.g., laboratory results) in the EHR data.

Third, all ILD patients included in this study were enrolled in a health plan (i.e., commercial, Medicare, or Medicaid) during the study period; thus, findings from this study may not be applicable to uninsured populations and patients with health plans not represented in the database.

Fourth, this study will minimize bias by utilizing propensity score matching on baseline variables (oxygen therapy versus no oxygen therapy cohorts) to examine outcomes of interest. Employing matching will enable a comparison of outcomes among patients who were similar on pre-ILD baseline characteristics. However, residual and/or unobserved confounding cannot be ruled out.

Finally, because medical and pharmaceutical claims are collected for the purpose of payment, there are inherent limitations to the use of claims databases for research. Coding errors may result in inaccurate or incomplete data, leading to potential misclassification of variables of interest and bias in research findings. A claim for a filled prescription is not an indication the medication was consumed or taken as prescribed. Also, physician-provided samples, samples taken as part of a clinical trial or over-the-counter medications will not be observed in claims data. Despite these limitations, claims data remain a robust and valuable source for the real-world examination of healthcare outcomes.

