7. RESEARCH METHODS

7.1 STUDY DESIGN

[figure not shown]
This is a non-interventional study of patients enrolled in a commercial, Medicaid, or Medicare plan, using existing administrative claims and EHR data in Optum's Market Clarity Integrated Claims + Clinical database for the period of 01 October 2015 through 30 June 2022 (study period). The study period may be extended through latest data available at the time of study implementation to increase study sample.

To describe the initiation and use of oxygen therapy after first fibrosing ILD diagnosis (**Aim 1**), patients aged ≥ 18 years with newly diagnosed fibrosing ILD will be identified from 01 October 2016 through 30 June 2022 (patient identification period). A schematic of the observation and identification periods is presented in Figure 1. Patients will be required to have 12 months of baseline continuous enrollment prior to fibrosing ILD diagnosis for collecting patient demographics and clinical characteristics. The pre-ILD baseline period will also be used to describe baseline prevalence of oxygen therapy use. Patients will be followed for a variable period from the fibrosing ILD diagnosis date (Section 7.2.2) until the earlier of disenrollment from the health plan, end of study period, or death. Oxygen therapy use will be described, and results will be stratified by underlying cause of fibrosis (e.g., IPF vs non-IPF ILD). Factors associated with initiation of oxygen therapy will be assessed using multivariable methods.

To assess the impact of oxygen therapy use on outcomes (**Aim 2 and Further Aim**), patients with fibrosing ILD who initiated oxygen therapy will be propensity score matched to those who did not yet initiate oxygen therapy. A schematic of the observation and identification periods is presented in Figure 2. The index date will be defined as the date of oxygen therapy initiation for oxygen therapy cohort, or a date that is eligible for index and is similar to the

[figure not shown]
matched case's index date for no oxygen therapy cohort. Disease progression, acute exacerbations, health care resource utilization (HCRU), and health care costs in the Aim 2 follow-up period will be described and compared between matched cohorts. Outcomes will be modelled using multivariable methods.

Figure 1. Observation and Identification Periods: Aim 1

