*The ILD diagnosis date will be defined as the first date of a claim with diagnosis for fibrosing ILD during the identification period. Patients will be followed from the fibrosing ILD diagnosis date until the earlier of disenrollment from the health plan, death, or end of the study period. Figure is not to scale and is for illustrative purposes only.

Figure 2. Observation and Identification Periods: Aim 2

*The fibrosing ILD diagnosis date will be before the index date and may be before or during the pre-index baseline period.

†The index date will be defined as the first date of a claim with oxygen therapy (oxygen therapy cohort), or a date that is eligible for index and is similar to the matched case's index date (no oxygen therapy cohort).

Patients will be followed from the index date until the earlier of disenrollment from the health plan, death, or end of the study period.

Figure is not to scale and is for illustrative purposes only.

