7.2.3 Study population: Aim 2 [REDACTED]

The analysis for Aim 2 and Further Aim will include patients identified for Aim 1 in Section 7.2.2 who meet the following additional selection criteria. Final oxygen therapy cohorts will be determined during the propensity score matching (PSM) procedure outlined in Section 7.6.2.2.

- **Oxygen therapy cohort**

- ILD patients with ≥ 1 medical claim for oxygen therapy after fibrosing ILD diagnosis. The ***index date*** will be defined as the first date of a claim for oxygen therapy.

- **No oxygen therapy cohort**
 - Matched to a patient in the oxygen therapy cohort. The **index date** will be assigned as a date that is eligible to set an index date (i.e., similar to the matched oxygen therapy patient in time from the fibrosing ILD diagnosis date to the index date, and during the same continuous enrollment period as the fibrosing ILD diagnosis date).

NOTE: Following review of results from Aim 1, the study team will determine whether criteria for Aim 2 and Further Aim require revision.

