7.3 VARIABLES

Variables related to the study period will be defined as follows:

Aim 1

- **Fibrosing ILD diagnosis date**—The first ILD diagnosis date for patients with ≥ 2 fibrosing ILD diagnoses on different dates and within 365 days. The fibrosing ILD diagnosis date is the first day of follow-up observation time for Aim 1.
- **Pre-ILD baseline period**—The 12-month period prior to the fibrosing ILD diagnosis date.
- **Aim 1 follow-up period**—The variable period starting on the fibrosing ILD diagnosis date and continuing until the earliest of the following: disenrollment from the health plan, death, or end of the study period. The Aim 1 follow-up period will be used to assess Aim 1 outcomes.
 - **All-cause mortality**—Death will be used as a censoring event and is further defined in Section 7.3.3.1.

Aim 2

- **Index date**—For the oxygen therapy cohort, the first date following the fibrosing ILD diagnosis date with a claim with diagnosis for oxygen therapy; for the no oxygen therapy cohort, a date within the same continuous enrollment period as the fibrosing ILD diagnosis date that is similar to the matched oxygen therapy patient in time from fibrosing ILD to index date. The index date is the first day of follow-up observation time for Aim 2 and Further Aim.
- **Pre-index baseline period**—The 12-month period prior to the index date.
- **Aim 2 follow-up period**—The variable period starting on the index date until the earliest of the following: disenrollment from the health plan, death, or the end of the study period. Matched pairs will be given the same duration of follow-up. The Aim 2 follow-up period will be used to assess Aim 2 and Further Aim outcomes.
 - **All-cause mortality**—Death will be used as a censoring event and is further defined in Section 7.3.3.1.

An overview of the analytic study variables and the study periods for which each analytic variable will be reported is provided in Table 1. Additional variable information is provided in Sections 7.3.1 to 7.3.4.

Table 1. Analytic Variables by Data Source and Time Period

Characteristic	Data source		Aim 1 time period		Aim 2 time period	
	Claims*	EHR	Pre-ILD baseline	Follow-up	Pre-index baseline	Follow-up
Aim 1 outcomes						
Oxygen therapy (time to initiation, sustained oxygen therapy use)		X		X	X	
Aim 2 outcomes						
Disease progression	X	X				X
All-cause mortality	X					X
Hypoxemia	X	X	X		X	X
Acute exacerbations	X	X				X
Patient characteristics†						
Index year	X		X		X	

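### Section 7.8 says the Aim 2 match balances pre-ILD baseline characteristics, which conflicts with the pre-index baseline that Section 7.3 and Table 1 define for Aim 2; the matching window must be named

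*Combined protocol and SAP*

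**What the plan says.** Section 7.8 (Limitations) presents matching as the protection against bias in the oxygen comparison and describes its result: "Employing matching will enable a comparison of outcomes among patients who were similar on pre-ILD baseline characteristics". The sentence before it refers only to baseline variables and names no window.

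Section 7.3 defines two baseline windows:

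- Pre-ILD baseline, listed under Aim 1: "The 12-month period prior to the fibrosing ILD diagnosis date".
- Pre-index baseline, listed under Aim 2: "The 12-month period prior to the index date".

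Table 1 marks each patient, clinical and utilization covariate it lists in both windows. It places the pre-ILD column under Aim 1 and the pre-index column under Aim 2. Section 7.3.5 has clinical characteristics measured in both windows and does not say which set enters the propensity score.

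On timing, the footnote to Figure 2 (Section 7.1) states: "The fibrosing ILD diagnosis date will be before the index date and may be before or during the pre-index baseline period". Section 7.2.3 admits to the oxygen cohort anyone with at least one "medical claim for oxygen therapy after fibrosing ILD diagnosis" and sets no upper limit on the delay. The comparator's index date is chosen to give a similar time since diagnosis. Section 7.2.3 refers to Section 7.6.2.2 for the matching procedure, and that section is not in the public text.

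**The concern.** Section 7.8 uses a defined Aim 1 term to describe an Aim 2 procedure. For covariates that hardly change, such as sex, or that are taken from the whole study period, such as underlying ILD type, the window makes no difference. It does matter for acute respiratory failure, pulmonary hypertension, admissions, medication use, comorbidity score and costs, all of which can change between diagnosis and oxygen start.

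Section 5 ties oxygen to breathlessness and resting hypoxemia, so deterioration after diagnosis plausibly prompts its use. If the propensity score used only pre-ILD values, a patient who went into respiratory failure after diagnosis and then started oxygen could be paired with one who stayed stable. The pair would look balanced. The difference in severity would then carry into mortality, progression, exacerbations and hypoxemia, and would make oxygen look harmful or hide a benefit. Giving the comparator the same time since diagnosis equalizes disease duration, not severity.

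**Working it through.** The plan gives no figure on this point to reproduce. The check is date arithmetic on the stated periods, followed by an illustration whose parameters are all assumptions.

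**1. How far apart the windows can be.** Inputs from Section 7.1: study period 01 October 2015 to 30 June 2022; identification period from 01 October 2016.

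- Longest possible gap from diagnosis to oxygen start: 01 October 2016 to 30 June 2022 = 2,098 days; 2,098 / 365.25 = 5.74 years, about 69 months.
- Earliest day of a pre-ILD baseline to the latest index date: 01 October 2015 to 30 June 2022 = 2,464 days = 6.75 years.

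These are calendar extremes, not typical values. A patient at the extreme would have essentially no follow-up.

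**2. Overlap of the windows.** With a gap of g months, overlap = max(0, 12 − g) months.

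- g = 3: 9 months shared
- g = 6: 6 months shared
- g ≥ 12: none

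Whatever the overlap, the g months between diagnosis and index are absent from the pre-ILD window.

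**3. What the documents say about g.** Table 3 counts 214,725 of 1,179,017 patients (214,725 / 1,179,017 = 18.2%) with oxygen evidence in the 12 months after first diagnosis. The count uses looser criteria than the study and does not show how many start later. The distribution of g is therefore unknown.

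**4. Illustration.** Assumptions:

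- 200,000 patients per run, with severity N(0,1) at diagnosis.
- Mean worsening of 0.3 SD per year; SD of the individual slope 0.2 or 0.5.
- Oxygen-start hazard of 0.1 × exp(β × current severity) per year; β = 0.5 or 1.0.
- Controls are still off oxygen at the same time since diagnosis and are nearest-matched on severity at diagnosis.

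Standardized difference in severity at index:

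| Gap | slope SD 0.2, β 0.5 | 0.2, 1.0 | 0.5, 0.5 | 0.5, 1.0 |
|---|---|---|---|---|
| 3 months | 0.004 | 0.001 | 0.016 | 0.015 |
| 1 year | 0.017 | 0.049 | 0.113 | 0.254 |
| 2 years | 0.059 | 0.195 | 0.349 | 0.728 |
| 4 years | 0.261 | 0.547 | 0.880 | 1.322 |

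The difference at diagnosis was 0.00 in every run. Matching on severity at index instead gave about 0.00 at index in every run.

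**5. Rough translation to mortality.** Assume a mortality log hazard ratio of 0.4 to 0.7 per SD of severity and no true oxygen effect. False rate ratio ≈ exp(log hazard ratio × difference).

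- 1 year: exp(0.4 × 0.017) = 1.01 to exp(0.7 × 0.254) = 1.19
- 2 years: exp(0.4 × 0.059) = 1.02 to exp(0.7 × 0.728) = 1.66

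A simpler model has no time axis and assumes a correlation of 0.3 to 0.8 between severity at diagnosis and at index. It gave residual differences of 0.34 to 0.80 SD and false rate ratios of 1.14 to 1.71. The gap enters that model only through the assumed correlation, so I give it less weight.

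**The case against.** The strongest reply is that Section 7.8 is a limitations paragraph, not the specification. The matching rule belongs to Section 7.6.2.2, which the public text omits. The reference list keeps a propensity score citation and the abbreviations keep IPTW, neither used in the visible text, so the omitted pages probably describe the method. The visible operative material, Section 7.3 and Table 1, points to the pre-index window for Aim 2. The simplest reading is that pre-ILD in Section 7.8 is a slip for pre-index.

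Most of this stands. A reader might infer that the study matches on pre-ILD covariates and that Aim 2 is therefore confounded by design. The documents do not show that: no visible passage assigns pre-ILD values to the propensity score. Nor can it be said that the plan omits the matching window, because text withheld from the public version is not missing from the plan. A reader might also infer from the 69-month maximum that gaps of years are usual, and nothing supports that.

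What remains is that two visible statements disagree and no visible passage reconciles them. The multivariable outcome modelling in Section 7.1 names no covariate window. The caveat in Section 7.8 on residual and unobserved confounding is general. It does not excuse leaving unbalanced the pre-index covariates that the plan already intends to measure.

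**Conclusion.** This is an internal inconsistency that should be reconciled, not a demonstrated design flaw. Section 7.8 names the Aim 1 window for the Aim 2 match, while Section 7.3 and Table 1 give Aim 2 its own.

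If the wording is a slip, the harm is a wrong description that could pass into the report. If it is literal, measured worsening after diagnosis is unbalanced in the main Aim 2 contrast. The effect is then negligible when oxygen starts within a few months of diagnosis. It could be material, and toward apparent harm from oxygen, when the gap is a year or more. The size depends on how fast patients worsen, how strongly severity drives oxygen start, and how gaps are distributed. The documents give none of these, so the simulated figures show what is possible and do not estimate bias in this study.

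**What to change.** In Section 7.8, change the description to pre-index baseline characteristics, so that it agrees with Section 7.3 and Table 1. Confirm in the matching section that the Aim 2 propensity score, the balance checks and the outcome-model covariates all use the 12 months before each member's index date. Pre-ILD values may be added as further covariates but should not replace the pre-index ones. If the matching section already says this, only Section 7.8 needs correcting.

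The cost is wording: Table 1 already plans the pre-index covariates, so no new data are needed. Balance may be slightly harder to reach, and a few more oxygen patients may go unmatched. The change addresses measured covariates only. FVC, DLCO and SpO2 are not in the visible covariate list (Sections 7.3.5.1 to 7.3.5.3), so naming the right window would not by itself balance physiological severity, and the caveat on residual confounding should stay.

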8. PROTECTION OF HUMAN SUBJECTS

This is a retrospective database study, and the data extracts will be fully de-identified and HIPAA compliant. No BIPI or Optum personnel will have the ability to link data to an identifiable individual. Data extraction will follow Optum policies and procedures for safety and security. Optum is responsible for all data extraction, analyses and storage. No raw claims data will be distributed to BIPI; only aggregated data will be shared with BIPI. Informed consent is not necessary due to the retrospective and non-invasive nature of the study.

9. MANAGEMENT AND REPORTING OF ADVERSE EVENTS/ADVERSE REACTIONS

AE collection not required for this study which is based on secondary use of data. The study does not include chart abstraction. There is no review of individual records to collect safety data to address the study objective.

10. PLANS FOR DISSEMINATING AND COMMUNICATING STUDY RESULTS

One or more abstracts/posters may be developed and submitted to relevant scientific conference(s) and one or more manuscripts will be developed (upon request) and submitted to relevant peer-reviewed medical journals mutually agreed by all study authors.

Both Optum and BIPI teams will convene a meeting to discuss the study results and develop a plan to disseminate the study findings through conference abstracts/posters presentations and journal manuscripts. All dissemination activities are optional and will be activated after data analyses.

Authorship will follow the guidelines proposed by the International Committee of Medical Journal Editors (ICMJE; www.icmje.org). All authors should meet the criteria for authorship, and all people who meet the criteria should be authors. Any potential conflicts of interest will be disclosed.

ANNEX 1. LIST OF STAND-ALONE DOCUMENTS

Number	Document Reference Number	Date	Title
1	None	N/A	N/A

ANNEX 2. ENCEPP CHECKLIST FOR STUDY PROTOCOLS

ANNEX 3. TABLE SHELLS

Table shells

ANNEX 4. CODE LISTS

Code lists

RX code lists

